##### **B. Randomization**

We will use the high quality pseudo-random deviate generator in SAS® (SAS Institute, Inc., Cary, North Carolina) to randomize participants to MACRO or SOC in 1:1 ratio with random block sizes chosen from small even numbers. Exact block sizes will be revealed to the rest of the study team at the conclusion of the study to prevent educated guessing. There are some key demographic differences in populations served by the study sites, as described in the Study Settings section. Thus, randomization will be stratified by site to ensure a balance between the treatment groups with respect to site by design rather than chance. To retain maximum degree of flexibility in post-COVID-19 environment, no other stratification criterion will be employed. The statistician will create schedules which link the randomization sequence number and treatment arm and will provide them to the team constructing the data management system. At randomization, a study team member will establish the link between the participant study identifier and randomization sequence number by clicking on a database function. Randomization data will only be visible to the study statistician and intervention delivery personnel. Therefore, all personnel involved in post assessments will be blind to treatment assignment.

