C. **Statistical Analyses.** Overview-We will perform all main analysis based on intention-to-treat philosophy following the a priori plans outlined below. All statistical analyses will be performed and overseen by the study statistician [name] using SAS® version 9 (SAS Institute, Inc., Cary, North Carolina). Participant flow will be summarized using a CONSORT diagram. Data will be summarized by treatment group and time point as well as baseline to follow-up change using appropriate descriptive statistics. First, the baseline participant characteristics will be compared between the two arms. Any significant differences will be noted and accounted for as additional covariates in the sensitivity analyses. Second, main analyses to address the aims will be performed as outlined below. Confirmatory hypothesis testing will be performed using multiple imputation for missing data. Third, a set of sensitivity analyses including additional covariates and ignoring missing data will be performed to evaluate the robustness of our findings.

**Baseline Comparisons**-Due to the randomization scheme balanced with respect to study site and the large sample size, it is unlikely that other baseline participant characteristics will be significantly different between the arms. However, we will control for any participant characteristics that are found to be significantly different by including them as additional covariates in the sensitivity analyses. In such an event, we will not alter the primary analytic strategy to preserve its a priori nature and predictability. We will use independent samples *t*-, Wilcoxon rank sum, chi-square and Fisher's exact tests, as appropriate based on distributional properties, and continuous/categorical nature of the characteristic being compared.

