**Aim 1 Analysis**-We will fit a series of linear mixed models using the SAS® MIXED procedure with baseline to follow-up changes in continuous outcomes as the dependent variable; intervention arm (MACRO/SOC), follow-up time point (3/6/12 months) and their interaction term as the fixed effects of interest; the baseline value of the continuous outcome as a fixed effect covariate; and a participant random effect to account for multiple measurements over time from the same participant. We will appropriately construct means contrasts to estimate MACRO vs SOC at each follow-up time point. The magnitude and statistical significance at  $\alpha=0.05$  of the MACRO vs SOC difference at 3 months for AM-PAC CAT Basic Mobility Domain will serve as the formal test of the primary hypothesis H1.1. If significant, we will define a meaningful responder as having at least a 2.60 point improvement in AM-PAC CAT Basic Mobility Domain over 3 months, compute percentage of responders in both arms, and conclude a number-needed-to-treat (NNT) as the reciprocal of the difference in percentages. We will employ the same analytic strategy described above for each of our secondary continuous outcomes such as physical activity, depression, frailty, self-efficacy and quality of life (H1.2). For the secondary outcomes measured only once at 3 months such as participation, adherence and satisfaction (H1.3), we will consider using Wilcoxon rank sum, chi-square and Fisher's exact tests to make between-intervention comparisons, depending on the categorical/ordinal/interval nature of the outcomes and their propensity for ill-behaved distributional properties. For count outcomes such as falls, number of medications, readmissions and hospitalizations in H1.4, we will fit a series of negative binomial regression models with the count outcome as the dependent variable; exposure time for the counts as an offset; a log link function; and intervention arm as the main independent factor of interest; and a marker of history of the outcome at baseline as a covariate MACRO vs SOC incident rate ratio and its statistical significance will serve as tests of H1.4.

**Aim 2 Analysis**-In the linear mixed models described above for H1.1 and H1.2, we will examine the between-intervention means contrasts at 6- and 12-months. The magnitude and statistical significance of the MACRO vs SOC arm differences at 6 and 12 months will serve as the formal test of the hypothesis H2.1.

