**Missing Data**-The best approach for handling missing data is prevention, and our clinical trials have had a low missingness rate. We will clearly document missing data and reasons in the CONSORT diagram and compare those with missing data to complete data at the follow-up assessments using the same methods outlined under *Baseline Comparisons* subsection above. We will use methods such as multiple imputation which consider the uncertainty involved in imputing missing data. Multiple imputation is arguably the best method to account for missing data under the ignorable or missing-at-random (MAR) assumption, and mitigates bias even when missing data is non-ignorable. Specifically, we will generate M=5 imputed values for each missing value, analyze the 5 datasets as though complete, and finally combine the results appropriately so that they reflect the uncertainty involved in imputation. SAS® MI and MIANALYZE procedures will be used. Other approaches to missing data will also be considered in sensitivity analyses.

**Sensitivity Analyses**-We will perform sensitivity analyses to examine the robustness of our results against various assumptions, such as fitting zero-inflated models or using dichotomous (any/none) operational definitions and logistic regression models. In addition, if analyses of residuals from the linear mixed models show violations of statistical assumptions, we will consider fitting models after Box-Cox transforming the continuous variables to make them approximately conform to a normal distribution.

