#### D. Sample Size and Power.

**Sample Size Justification.** We base our sample size on published data, published statistical methods, and commercially available software (SAS® POWER procedure; SAS Institute, Inc., Cary, North Carolina). Between-subject standard deviation of the baseline to follow-up change in the primary outcome AM-PAC CAT Basic Mobility Scale is approximately 7.97 in rehabilitation outpatients. We consider 2.60 points a minimally clinically important difference based on MDC68. We plan to randomize 187+187=374 participants, anticipating 149+149 completers assuming a conservative 80% retention rate. We can detect a between treatment arm difference of 2.60 points in AM-PAC CAT Basic Mobility Scale with 80% statistical power in a two-tailed test at  $\alpha=0.05$ . This difference is smaller than the actual observed changes previously reported, indicating ample statistical sensitivity. The logistic regression model proposed in Aim 3 requires a minimum of about 5-10 events per variable, and assuming a half in the MACRO group responds, we would be able to fit a multivariable model with at least 15 variables. Thus, we are confident of the adequacy of sample size to address all aims.

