## **17.0 Number of Subjects**

### **Recruitment.**

We will randomize approximately 374 participants, approximately 40 at the University of Pittsburgh over approximately 24-months, allowing for a 20% drop-out at 52-week follow-up.

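### The primary mixed model names only a participant random effect, so with default residuals the 3-month test of H1.1 relies on equal variance at 3, 6 and 12 months; site, the only stratum, is also left out (minor)

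*Combined protocol and SAP*

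**What the plan says.** Section 9.1 C, Aim 1 Analysis, fits SAS PROC MIXED to change from baseline. The model has "intervention arm (MACRO/SOC), follow-up time point (3/6/12 months) and their interaction term as the fixed effects of interest". The remaining terms are "the baseline value of the continuous outcome as a fixed effect covariate; and a participant random effect to account for multiple measurements over time", so the participant random effect is the only term for the repeated measurements. The MACRO versus SOC contrast at 3 months from this model is the formal test of H1.1, at a two-sided 0.05 level. The 6- and 12-month contrasts from the same model test H2.1.

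Other places that bear on the point:

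- **Overview, section 9.1 C:** "Confirmatory hypothesis testing will be performed using multiple imputation for missing data". Extra covariates enter only sensitivity analyses, and only if they differ significantly between arms at baseline.
- **Sensitivity Analyses, section 9.1 C:** if residuals violate the assumptions, "we will consider fitting models after Box-Cox transforming the continuous variables" to bring them closer to normality.
- **Section 9.1 D:** "Between-subject standard deviation of the baseline to follow-up change in the primary outcome AM-PAC CAT Basic Mobility Scale is approximately 7.97". No time point is attached to this SD.
- **Section 17.0:** the target is described as "allowing for a 20% drop-out at 52-week follow-up".
- **Section 3.1 B:** "randomization will be stratified by site to ensure a balance between the treatment groups with respect to site by design rather than chance". No other stratification factor is used, and site does not appear in the Aim 1 model.

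The plan names no residual covariance structure, visit-specific variance, robust standard error or degrees-of-freedom method.

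**The concern.** A participant random effect with default residuals is a compound-symmetry model: one variance at every visit and one correlation between any two visits. The 3-month estimate itself is sound, but its standard error is built from the variance pooled over 3, 6 and 12 months. The primary test therefore depends on how variable patients are at visits that the primary hypothesis does not concern.

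The direction of the error depends on how the spread changes. If it grows over the year, the 3-month standard error is too large and the test loses power. If it narrows, the standard error is too small and type I error exceeds 5%. Nothing in the plan shows that the spread is constant. Participants are aged 70 or older and are enrolled as inpatients or within about 90 days of an acute event, whereas the single SD comes from rehabilitation outpatients.

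The stated safeguards do not reach this. A Box-Cox transformation aimed at normality is not a provision for variances that differ by visit. Multiple imputation does not help either, because each completed dataset is analysed with the same model.

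Omitting site is a separate and smaller matter. Stratified randomisation removes between-site variation from the true error of the comparison, but a model without site leaves that variation in the estimated error. The rule for adding covariates would rarely bring site in, because stratification makes a significant imbalance unlikely.

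**Working it through.** **Inputs from the plan (sections 9.1 C, 9.1 D and 3.1 B).** Difference 2.60; SD of change 7.97; two-sided α = 0.05; 187 randomised and 149 completers per arm; M = 5 imputations; randomisation stratified by site.

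**Assumptions, because the documents give no figures.** SDs at 6 and 12 months; the share of variance due to site; the correlation between visits; retention at 3 months.

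**1. The plan's own figure.** SE = 7.97 × √(2/149) = 0.923. Then 2.60/0.923 = 2.816, and power = Φ(2.816 − 1.960) = 80.4% (80.1% with the noncentral t). Allowing for 20% loss gives 187 per arm, 374 in total. The stated sample size reproduces.

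**2. Equal-variance dependence, complete data.**

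- True SE at 3 months = SD₃ × √(2/n).
- Model SE = √[(SD₃² + SD₆² + SD₁₂²)/3] × √(2/n).
- k = 1.96 × (model SE / true SE).
- Type I error = 2 × (1 − Φ(k)); power = Φ(2.60/true SE − k).

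Example, SDs 7.97/9/10: mean variance = (63.52 + 81 + 100)/3 = 81.51, so model SE = 9.028 × √(2/149) = 1.046 against a true 0.923. Then k = 2.220, type I error = 2.6%, and power = Φ(2.816 − 2.220) = 72.4%.

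| SD at 3/6/12 months | Model SE / true SE | Type I error | Power, 149 per arm |
|---|---|---|---|
| 7.97/7.97/7.97 | 1.000 | 5.0% | 80.4% |
| 7.97/8.5/9 | 1.067 | 3.7% | 76.6% |
| 7.97/9/10 | 1.133 | 2.6% | 72.4% |
| 7.97/7.5/7 | 0.941 | 6.5% | not comparable |
| 7.97/7/6 | 0.883 | 8.4% | not comparable |

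Power is not comparable in the last two rows because the test does not hold its level.

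Fitting random-intercept REML models to simulated data (mean of 12 fits, 149 per arm) confirms the formula: SE 1.037 against 1.046 for 9/10, and 0.814 against 0.815 for 7/6.

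**3. Better retention at 3 months.** Section 17.0 places the 20% loss at 52 weeks. If 10% were lost by 3 months, 187 × 0.9 ≈ 168 per arm would be seen. Power would then be 81.6% (8.5/9) and 77.9% (9/10), against about 85% with a visit-specific variance.

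**4. With multiple imputation.** Simulation settings: 187 per arm, visit correlation 0.6, monotone missing completely at random, M = 5, Rubin's rules with Barnard-Rubin degrees of freedom, 4,000 trials per setting. Monte Carlo SE is 0.3–0.4 points for type I error and 0.6–0.7 for power. With 20% missing at each visit:

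| SD at 6/12 months | Type I error, random effect only |
|---|---|
| equal | 5.6% |
| 8.5/9 | 3.9% |
| 9/10 | 2.9% |
| 7.5/7 | 5.8% |
| 7/6 | 7.9% |

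An unstructured covariance gave 4.7–5.6% across these settings. Power for 9/10 was 70.5% with the random effect and 76.9% unstructured.

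With 10/15/20% missing at the three visits, type I error was 3.0% (9/10) and 7.6% (7/6), against 5.4% and 4.9% unstructured. Power for 9/10 was 76.6% against 82.8%.

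**5. Effect on Aim 2.** The step 2 formula applied to the 12-month contrast, with SD₁₂ in the true SE, gives type I error of 6.4% (8.5/9) and 7.7% (9/10). A rising spread therefore makes the 3-month test conservative and the 12-month test too liberal.

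**6. Site.** Total SD 7.97, 149 per arm. True SE = 7.97 × √[(1 − share) × 2/149]; model SE without site = 0.923.

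| Assumed site share | Type I error, site omitted | Power without site | Power with site |
|---|---|---|---|
| 2% | 4.8% | 80.6% | 81.2% |
| 5% | 4.4% | 81.0% | 82.4% |
| 10% | 3.9% | 81.6% | 84.3% |

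The baseline covariate may already absorb part of any site difference.

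**The case against.** The strongest reply is that this is silence rather than error. PROC MIXED can combine a participant random effect with visit-specific residual variances, and the plan does not say the residuals are homogeneous. Nothing in the documents points to unequal variances, and if they are equal no harm follows. This is fair, and it is why the point is conditional on default residuals. But the test of H1.1 is meant to be fixed in advance, and the only structure named is the restrictive one.

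Second, the calculations above use the raw SD of change, whereas the model adjusts for baseline. With an assumed baseline-to-change correlation of 0.3, closed-form power is 83.9% (equal SDs), 80.6% (8.5/9) and 76.8% (9/10). With 0.4 it is 86.7%, 83.7% and 80.3%. So power need not fall below 80%, although the relative loss remains. Type I error is unaffected if baseline explains the same share of variance at each visit. A separate M = 5 simulation with baseline in the model kept the same direction: about 2% for rising SDs and 6–7% for falling SDs, Monte Carlo SE about 0.5 points.

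Third, 12-month data are collected only as study length allows. If half were observed and the rest not imputed, an approximate weighting gives 3.0% instead of 2.6% (9/10) and 7.6% instead of 8.4% (7/6). The effect shrinks but stays.

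Fourth, under imputation a mild narrowing (7.5/7) gives 5.8% against 5.6% for equal SDs, which is no detectable difference. Clear inflation needs a fall of about a quarter, from 7.97 to 6. This stands.

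Finally, the list of sensitivity analyses is open-ended and could include a covariance check. It does not commit to one, and a sensitivity analysis would not change the formal test.

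**Conclusion.** The concern holds. As written, and with default residuals, the test of H1.1 has its nominal level only if the variance of change is the same at 3, 6 and 12 months, and the plan neither supports that nor provides for its failure.

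The size depends entirely on later-visit SDs that the documents do not give. Over the range tried, closed-form type I error runs from 2.6% to 8.4%, and power falls by up to 8 points (80.4% to 72.4%) when the spread grows. Multiple imputation, baseline adjustment and incomplete 12-month data reduce these effects without removing them. With equal SDs there is no error. The same model carries the formal 6- and 12-month tests, so a steady change in spread in either direction pushes the 3-month or the 12-month test above 5%.

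The omission of site is real but minor. It errs on the conservative side, leaves the promised 80% power intact, and costs 0.5 to 2.7 points of power for assumed site shares of 2 to 10%.

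Neither part affects the stated sample size. The change is worth making because it costs almost nothing and removes a dependence that cannot be checked before the data are in.

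**What to change.** In the Aim 1 and Aim 2 mixed models:

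- Replace the participant random effect with an unstructured within-participant covariance over 3, 6 and 12 months (REPEATED statement, TYPE=UN), with Kenward-Roger degrees of freedom.
- Name in advance a fallback for non-convergence that still lets the variance differ by visit, such as heterogeneous compound symmetry (TYPE=CSH).
- State that the same model is fitted in every imputed dataset.
- Add site as a fixed effect.

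The cost is two lines of SAP wording, four more covariance parameters (six instead of two), and one degree of freedom for each site beyond the first; the documents do not state the number of sites. No new data are needed, and the sample size and power statement stay as they are. The wording should be settled before unblinded outcome data are seen, so that the structure is not chosen in the light of the result.

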### Specific Aims/Hypotheses

**Aim 1:** To establish efficacy, safety and acceptability of the MACRO intervention via a RCT.

We hypothesize that after 3 months, compared to standard of care (SOC), participants randomized into the MACRO arm will have:

H1.1: Greater improvements in function as measured by Activity Measure for Post-Acute Care Computer Adaptive Test (AM-PAC-CAT) Basic Mobility Domain (primary outcome).

H1.2: Greater improvements in function as measured by accelerometry; AM-PAC CAT Daily Activity Domain; depression; frailty; self-efficacy; and quality of life. These will be collected to the extent possible in respect to local limitations that may result from fluctuations in COVID-19 prevalence.

H1.3: Greater CR participation and adherence.

H1.4: Greater impact in readmissions and hospitalization.

**Aim 2:** To examine the duration of benefit of MACRO compared to SOC.

H2.1: We hypothesize that relative MACRO benefits (i.e., function indices (see H1.2), adherence and readmissions/hospitalization will persist after 6 and 12 months (12 months will be captured as timing allows)

**Aim 3:** To explore characteristics of patients who benefit the most from the MACRO intervention.

H3.1: We anticipate functional capacity and other baseline characteristics will identify those who benefit from the MACRO intervention (exploratory).

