**Table 1. Data Collection Plan**

Study Measure	Baseline	3, 6, 12 months
Risk assessment	X	
AM-PAC CAT Basic Mobility Domain (primary outcome)	X	X
Accelerometer	X	X
AM-PAC CAT Daily Activity Domain	X	X
3 Day Food Record (not at WU site)	X	X
Questionnaires	X	X
CR adherence/attendance		X
Reduced falls, medication burden, readmissions and hospitalization	X	X

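### The count-outcome rule gives number of medications an exposure-time offset and an incident rate ratio, although it is a state at a visit and not a count that accrues with time

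*Combined protocol and SAP*

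**What the plan says.** The rule is in section 9.1 C, Aim 1 Analysis. It opens "For count outcomes such as falls, number of medications, readmissions and hospitalizations in H1.4" and specifies a series of negative binomial regressions with a log link, "exposure time for the counts as an offset", study arm as the factor of interest, and a marker of baseline history as covariate. The result is defined for the whole group: "MACRO vs SOC incident rate ratio and its statistical significance will serve as tests of H1.4". No exception is made for medications. The sensitivity analyses later in 9.1 C (zero-inflated models, any/none outcomes with logistic regression) do not remove the offset.

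The collection sections treat the outcomes differently:

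- **Falls and admissions.** Section 7.2, items G and I, asks at each follow-up about falls and hospital care since the previous contact. These are events over an interval.
- **Medications.** Table 1 has the row "Reduced falls, medication burden, readmissions and hospitalization", collected at baseline and at 3, 6 and 12 months. Section 7.2, item H, defines deprescribing-eligible medications (DEMs) as a pre-identified list. The de-prescribing paragraph of section 7.2 describes a medication review at baseline. All of these describe what a participant is taking at a given time.

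On timing, the Aim 1 hypotheses share the stem "We hypothesize that after 3 months, compared to standard of care (SOC), participants randomized into the MACRO arm will have". Under that stem stands "H1.4: Greater impact in readmissions and hospitalization", which does not mention medications. H2.1 says that "adherence and readmissions/hospitalization will persist after 6 and 12 months", again without medications. The Aim 2 Analysis extends only the continuous-outcome models: "In the linear mixed models described above for H1.1 and H1.2, we will examine the between-intervention means contrasts at 6- and 12-months". The count-model sentence itself names no visit.

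**The concern.** A log-exposure offset asserts that the expected count is proportional to the time observed. That is reasonable for falls and admissions. It is not reasonable for a list of current medications: a participant taking ten drugs at week 11 and another taking ten at week 15 have the same burden, yet the offset gives them different rates.

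Two things are at stake. One is interpretation, because an incident rate ratio for medications reads as a ratio of new prescriptions per unit time, which nothing in the plan measures. The other is precision, because dividing by time adds the spread of visit times to an outcome that does not depend on them. De-prescribing is an explicit part of the MACRO intervention, so the medication result should be readable on its own terms.

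**Working it through.** **The plan's own figure.** The documents state no effect size, variance or power for any count outcome, so there is nothing to reproduce for this point. The only sample-size figure is for the primary outcome: 2 × (1.960 + 0.842)² × 7.97² / 2.60² ≈ 148 per arm by the normal formula and 149 by the t-test, and 149 / 0.8 = 186.25, rounded up to 187 per arm, or 374. It reproduces, and the count rule does not enter it.

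**Inputs.** From the documents: 187 per arm, 1:1 allocation, two-sided 5% level. Assumed, because the documents give none: mean 8 medications; between-person coefficient of variation (CV) 0.15, 0.32 or 0.50 with Poisson variation added; 30% or 80% of baseline medications still taken at follow-up; 3-month visits spread evenly over 11 to 15 weeks; true ratio 1.00 or 0.90.

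**Step 1: equal exposure.** With the same time c for everyone, log(mean) = log c + b0 + b1 × arm + … . The term log c goes into the intercept and b1 does not change. A direct comparison under equal exposure gave the same estimate (0.997) and standard error (0.0412) with and without the offset.

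**Step 2: hand check for 11 to 15 weeks.** SD of time = 4/√12 = 1.155 weeks. SD of log time ≈ 1.155/13 = 0.089, variance 0.0079. The squared CV of the count is v = 1/8 + CV². Before baseline adjustment, the SD of the log ratio grows by about √(1 + 0.0079/v):

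| CV | Total SD (8√v) | v | SD ratio |
|---|---|---|---|
| 0.15 | 3.1 | 0.1475 | 1.03 |
| 0.32 | 3.8 | 0.2274 | 1.02 |
| 0.50 | 4.9 | 0.3750 | 1.01 |

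Baseline adjustment shrinks the residual variation, so the added 0.0079 weighs more. With 80% of 8 medications retained, the conditional variance is 8 × 0.8 × 0.2 = 1.28 for retained drugs plus 8 × 0.2 = 1.6 for new ones, or 2.88. Then v = 2.88/64 = 0.045 and the SD ratio is √(1 + 0.0079/0.045) = 1.08.

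**Step 3: simulation at the 3-month visit.** Negative binomial fits with and without the offset gave an SD ratio of 1.01 to 1.12 across settings. Power for a ratio of 0.90 was lower by about two points or less. In a typical setting (CV 0.32, 30% retained, yes/no baseline marker) the SD ratio was 1.03 and power 66% with the offset against 68% without. Estimated ratios were within 0.01 of the truth. A smaller mean, as a DEM count might have, does not raise the cost: with CV 0.5, 30% retained and the yes/no marker, the SD ratio was 1.01 at means of 8, 2 and 1.

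**Step 4: does dropping the offset suffice?** Not by itself. In the 80%-retained case the conditional variance is 2.88 against a mean of 8, a ratio of 0.36. A negative binomial model cannot represent a variance below the mean, so its standard error is too large by about 1/√0.36 = 1.67. The nominal 1.96 threshold then acts like 1.96 × 1.67 = 3.27, a two-sided level near 0.1%. In simulation, null rejection with model-based errors and adjustment for the baseline count was 0 to 0.3%. With robust errors or a linear model it was 3 to 7%. Multiple imputation, which the plan intends, was not simulated.

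**The case against.** The strongest reply is that at 3 months almost nothing goes wrong. The offset is nearly constant there, most of it goes into the intercept, and a careful analyst might set exposure to one for a point-in-time count. The first part stands and fixes the size of the point: what is left is mainly a wrong label on a secondary outcome that the Aims section does not name. The second part is a possible reading only. The plan does not say it, and 9.1 C commits to following its a priori rules.

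A second reply is that the medication count is never defined, so it might be a count of drugs started or stopped over an interval, which would accrue. No section gives such a definition, and Table 1, the DEM item and the medication review all point to a state. The gap is a reason to add the definition.

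In the other direction, a reader might infer a serious loss of power or even bias. Section 5.0 gives 26 to 52 weeks of participation, and the count-model sentence names no visit. If half of each arm contributed a 26-week and half a 52-week count, a comparison with an assumed mean of 10 medications put power for a ratio of 0.90 at 49% with the offset against 73% without. If 20% of MACRO and 30% of SOC had the short exposure, the offset gave a ratio of 0.93 and 30% false rejections where there was no effect. The documents do not support either inference. They describe no pooling of counts from visits of differing length and no difference in follow-up between arms, they plan multiple imputation for missing data, and the hypothesis wording points to 3 months.

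**Conclusion.** The point holds as a minor one. Section 9.1 C, as written, applies an exposure-time offset and an incident rate ratio to an outcome that does not accrue with time. On the 3-month reading the cost in precision is slight: SD of the log ratio about 1.01 to 1.12 times as large, power lower by about two points or less, no bias. The main fault is that the reported quantity would be called a rate ratio when it is not one.

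These figures rest on assumed medication counts and visit windows, and the no-bias statement assumes that visit timing does not differ between arms. The cost would be larger only if counts from visits of differing length were combined, which the plan does not describe. The primary hypothesis test and the sample size of 374 are untouched.

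**What to change.** In section 9.1 C, Aim 1 Analysis:

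1. Restrict the exposure-time offset and the incident rate ratio to falls, readmissions and hospitalizations.
2. State whether the medication outcome is the DEM count of section 7.2, item H, or all current medications, and that it is taken at the 3-month visit.
3. Analyse that count without an offset, adjusted for the baseline count. Name one method in advance: either a log-link count model with robust (sandwich) standard errors, reporting a ratio of means, or the linear change model already planned for continuous outcomes, reporting a difference of means. Model-based negative binomial errors should not be used here, because a persistent count adjusted for its baseline is under-dispersed and the test would be far too conservative.

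The cost is one or two sentences and a slightly different model for one secondary outcome. No new data are needed.
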